8.7. Data Analysis

All measures described in [Section 8.3](#) will be summarized descriptively through the tabular and graphical display of mean values, medians, ranges, and standard deviations of continuous variables of interest and frequency distributions for categorical variables. Time-to-event outcomes (ie, overall survival, PFS, time to second-line initiation) will be described using the Kaplan-Meier method. All analyses will be conducted using SAS (version 9.4 or later) statistical software. Samples of patients who switched from the 4/2 to the 2/1 schedule from each country will be pooled and analyzed in aggregate. The sample of patients from Brazil who initiated first-line sunitinib on the 2/1 schedule will be analyzed separately. Results may be described for up to 2 subgroups that will be determined after the initial review of the data (eg, number of cycle on the 4/2 schedule).

As this study is descriptive and designed to generate hypotheses, direct comparisons between outcomes on the 4/2 schedule and on the 2/1 schedule will not be conducted. Potential confounders, such as characteristics that prompt the switch and other possible time-dependent factors (eg, dose modifications and delays), are not comprehensively collected or controlled for in this study design. Variability in timing of the switch from a 4/2 to a 2/1 schedule will affect the distribution of time-dependent outcomes after the switch (even in the absence of immortal-time bias), as some patients may switch “early” in their first-line therapy and others may switch “later.” Thus, causal inferences about the benefit of switching treatment schedules cannot be drawn.

PFIZER CONFIDENTIAL

Detailed methodology for summary and statistical analyses of data collected in this study will be documented in a statistical analysis plan, which will be dated, filed and maintained by the sponsor. The statistical analysis plan may modify the plans outlined in the protocol; any major modifications of primary endpoint definitions or their analyses would be reflected in a protocol amendment.

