Data Analysis: Analyses will include a descriptive summary of patient characteristics, first-line treatment patterns (eg, time to switch from 4/2 to 2/1; 4/2, 4/1, and total treatment durations), first-line disease progression from the start of 4/2 and the start of 2/1 schedules, AEs, and survival from the start of 4/2 and the start of 2/1 schedules. Time-to-event outcomes (ie, overall survival, treatment duration, PFS) will be described using the Kaplan-Meier method. Patients who initiated treatment on the 2/1 schedule will be analyzed separately from patients who switched from the 4/2 to 2/1 schedule.

Milestones: Key milestones include finalization of the protocol and case report form (quarter [Q]2 2019), initiation of site feasibility assessments (Q1 2019), initiation of the ethics review process (Q2 2019), start of data collection (to be determined; following completion of ethics review on a site-by-site basis), final interim analysis (Q3/Q4 2019), and final analytic results and final study report (to be determined based on site contracting timelines).

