7. RESEARCH QUESTION AND OBJECTIVES

This study consists of compiling and analyzing recent data from a customized retrospective medical record review conducted in 7 countries (Argentina, Brazil, Colombia, Costa Rica, Ecuador, Mexico, and Peru) to assess the following primary objectives:

- Describe demographic and clinical characteristics of patients in Latin America diagnosed with metastatic RCC who received first-line sunitinib and switched from the 4/2 to the 2/1 schedule.
- Characterize detailed first-line sunitinib treatment patterns, including dose, schedule, total duration of sunitinib treatment, duration on the 4/2 schedule, duration on the 2/1 schedule, reasons for stopping treatment lines, and supportive care.

The secondary objectives of the study will include an exploration of clinical outcomes (ie, response to treatment, AEs, PFS, and overall survival) after switching to the 2/1 schedule. Switching to the 2/1 schedule is a relatively new occurrence in the studied countries, resulting in limited available follow-up time to observe clinical outcomes among patients who switched to the alternative schedule. Furthermore, this study relies on a convenience sample of sites treating patients at a select number of treatment centers, will provide only descriptive information on observed events, and is designed to generate, not test, hypotheses. In Brazil, early feasibility results suggest physicians frequently prescribe sunitinib on the 2/1 schedule at first-line initiation; therefore, secondary objectives will also include a descriptive exploration of demographic, clinical and treatment characteristics (eg, duration of treatment, reasons for stopping treatment), and clinical outcomes (eg, treatment response, AEs, PFS, and overall survival) among patients initiating first-line sunitinib on the 2/1 schedule. It is anticipated this sample will be relatively small. Secondary objectives will be assessed with known limitations concerning data availability and generalizability of the findings.

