8.2.1. Patient Inclusion Criteria

1. Diagnosed with metastatic RCC with clear cell histology:
 - a. The patient may have been initially diagnosed with Stage IV or initially diagnosed at an earlier stage and progressed to having disease at distant sites (ie, metastatic disease).
2. Initiated first-line treatment for metastatic RCC with sunitinib on the 4/2 schedule (all countries) or initiated first-line treatment for metastatic RCC with sunitinib on the 2/1 schedule (Brazil only).
3. Switched to the 2/1 schedule (all countries) or initiated the 2/1 schedule (Brazil only) during the first treatment line between January 1, 2014, and June 30, 2018:
 - a. The final dates defining this selection period will be dependent on country-specific ethics and reporting requirements.
4. Aged 18 years or older at the time of the switch to the 2/1 schedule (all countries) or initiation of the 2/1 schedule (Brazil only).

PFIZER CONFIDENTIAL

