8.3.3. Treatment Patterns

Measures related to the treatment of RCC before (if applicable) and after diagnosis of metastatic RCC will be gathered. [Figure 2](#) graphically depicts the time periods during which treatment patterns will be assessed for each sample. Treatment measures may include the following:

- Receipt of broad categories of treatment approaches, including neoadjuvant treatment(s), surgery, and adjuvant therapy before the diagnosis of metastatic RCC:
 - Date of receipt of last cancer-direct treatment before the diagnosis of metastatic RCC.
- Total number of systemic lines of treatment after the diagnosis of metastatic RCC:
 - Start and stop dates of each treatment line (duration of each treatment line will be calculated).
- Specific details regarding first-line treatment with sunitinib after the diagnosis of metastatic RCC include the following (where relevant to the specific sample):
 - Start and stop dates of the 4/2 schedule (duration of 4/2 treatment);
 - Date of switch to or initiation of the 2/1 schedule and stop date (duration of 2/1 treatment);
 - Time between stopping the 4/2 schedule and initiating the 2/1 schedule;
 - Reason for switch to 2/1 schedule;
 - Date of subsequent changes in schedule, if any
 - Reason for subsequent changes in schedule, if any
- Initial and subsequent daily dose(s) of sunitinib on the 4/2 and 2/1 schedules:
 - Date(s) of dose change(s), if applicable;

PFIZER CONFIDENTIAL

- Reason for change(s) in dose, if applicable.
- Reason for stopping treatment with sunitinib (eg, AE, progressive disease);
- Best clinician assessed response to treatment with sunitinib on the 4/2 schedule and best response on the 2/1 schedule.
- Receipt of broad categories of supportive care elements (medications and procedures) such as nutritional supplements, pain medications, antibiotics, antifungals, iron supplements, antiemetics/antinauseants, antidiarrheals, antivirals, radiation therapy, bone-targeting agents (eg, bisphosphonates, denosumab), erythropoiesis-stimulating agents, granulocyte-colony stimulating factors, folic acid, red blood cell transfusion, and platelet transfusion during the first line of treatment with sunitinib.

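### Reasons for stopping sunitinib get only a frequency distribution, so the pooled percentages depend on unequal follow-up and on an unstated denominator; cumulative incidence by reason should be added

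*Combined protocol and SAP*

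**What the plan says.** Section 7 places stopping reasons in the second primary objective, which covers "duration on the 2/1 schedule, reasons for stopping treatment lines, and supportive care". Section 8.3.3 collects the item as a category, "Reason for stopping treatment with sunitinib (eg, AE, progressive disease", together with start and stop dates for each treatment line and for each schedule.

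Section 8.7 gives categorical measures a frequency distribution as part of the "tabular and graphical display of mean values, medians, ranges, and standard deviations of continuous variables of interest and frequency distributions for categorical variables". Methods that handle censoring are kept for other outcomes: "Time-to-event outcomes (ie, overall survival, PFS, time to second-line initiation) will be described using the Kaplan-Meier method". The abstract (Section 3) has a different list: "Time-to-event outcomes (ie, overall survival, treatment duration, PFS) will be described using the Kaplan-Meier method". So the abstract treats time on treatment as possibly censored and Section 8.7 does not list it. Neither list separates the reasons.

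On follow-up, Section 8.2.1 requires the switch, or in Brazil the initiation of 2/1, to fall "during the first treatment line between January 1, 2014, and June 30, 2018". The notes to Figures 2 and 3 allow follow-up to end at a date set by each site's ethics approval, and Section 5 starts the ethics process in Q2 2019. Section 7 describes switching as recent, "resulting in limited available follow-up time to observe clinical outcomes among patients who switched to the alternative schedule", although it says this of the secondary clinical outcomes.

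Nowhere do the documents give a denominator for stopping reasons, a category for ongoing treatment, or a rule for patients lost to follow-up. The limitations in Section 8.9 do not raise the matter.

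**The concern.** Stopping for an AE, for progression or for another cause are competing events in time. A patient still on sunitinib at the cut has no reason yet, and patients in this study would be observed for anything from about one year to more than five. A single pooled percentage mixes these lengths of observation.

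Two denominators are possible. With stopped patients only, reasons that act early have had time to appear and later ones have not, so early reasons take too large a share. With all patients, no reason is inflated, but any reason that can still occur is understated as a description of how treatment ends.

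Kaplan-Meier for total treatment duration, as in the abstract, does not answer this because it does not split the curve by reason. At stake is whether one of the items named in a primary objective can be read without knowing each site's follow-up, and whether it can serve as a baseline for later comparison, a use that Section 6 foresees.

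**Working it through.** **Nothing to reproduce.** The plan gives no expected share still on treatment and no expected split of reasons. The target of at least 150 records has no formula behind it. All scenarios below rest on assumptions.

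**Step 1: length of follow-up.** The selection window is 1 January 2014 to 30 June 2018, which is 54 months. With a cut at mid-2019 (assumed from the Q2 2019 ethics start), potential follow-up from the switch is 12 to 66 months.

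**Step 2: share still on sunitinib.** Assume exponential time on treatment from the switch with median M, and switch dates uniform over the window. With h = ln 2 / M and follow-up from a to b months:

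share ongoing = [exp(-ha) - exp(-hb)] / [h(b - a)]

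Section 6 gives a median PFS of 11 months on sunitinib, used here as a proxy for time on treatment. It also cites a registry with durations on 2/1 more than three times those on 4/2. I take 33 months (3 x 11) as an upper scenario and 22 months as an intermediate one.

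- M = 11: (0.4695 - 0.0156) / (0.0630 x 54) = 13.3%, about 20 of 150
- M = 22: (0.6852 - 0.1250) / (0.0315 x 54) = 32.9%, about 49 of 150
- M = 33: (0.7772 - 0.2500) / (0.0210 x 54) = 46.5%, about 70 of 150

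A cut six months later (18 to 72 months) gives 9.1%, 27.3% and 41.0%. If switches cluster late (12 to 36 months), the shares are 24.2%, 48.1% and 61.0%.

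**Step 3: effect on the AE share among stopped patients.** Let F_AE(t) and F_oth(t) be the cumulative incidences of stopping for an AE and for any other reason. The plain share among stopped patients is mean F_AE / (mean F_AE + mean F_oth), averaged over follow-up from a to b. The eventual share is F_AE at infinity. Three hazard patterns were assumed, with h = ln 2 / 11, ln 2 / 22 or ln 2 / 33:

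- proportional: AE 0.25h, other 0.75h
- AE early: AE 0.08 exp(-t/4) per month, other h
- AE late: AE 0.25h min(t/24, 2), other 0.8h

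| Pattern | h from | Eventual AE share | Among stopped, 12-66 months | Among stopped, 12-36 months |
|---|---|---|---|---|
| Proportional | any of the three | 25.0% | 25.0% | 25.0% |
| AE early | 11 | 22.3% | 24.6% | 27.0% |
| AE early | 22 | 24.5% | 32.2% | 37.6% |
| AE early | 33 | 25.4% | 38.3% | 45.6% |
| AE late | 11 | 15.9% | 13.4% | 10.9% |
| AE late | 22 | 23.0% | 17.1% | 12.5% |
| AE late | 33 | 26.8% | 18.7% | 13.2% |

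The difference runs from -8.1 to +12.9 points at 12 to 66 months and from -13.6 to +20.2 points at 12 to 36 months. It is zero under proportional hazards. The last two columns make the main point: the underlying process is the same in each row, yet outside the proportional case the percentage moves when only follow-up changes.

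**Step 4: all patients as denominator.** F_AE(t) cannot exceed its eventual value, so no share is inflated. In the proportional case with h from 11 months and 12 to 66 months of follow-up, AE stops are 21.7% of all patients against an eventual 25.0%, and 13.3% are ongoing.

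**Step 5: what fixed-time incidence does and does not give.** Suppose 20% eventually stop for an AE (exponential, mean 5 months) and 80% for other reasons (exponential, median 18 months). By 24 months the cumulative incidences are 0.2 x (1 - exp(-24/5)) = 19.8% for AE and 0.8 x (1 - 2^(-24/18)) = 48.3% for other reasons. The second is far from 80%, and rightly so: it is the probability by 24 months, not the eventual share.

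**The case against.** The best case for leaving the plan alone has four parts.

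- **The study is descriptive.** A list of recorded reasons at the cut is a valid description, and cause-specific incidence is an added quantity that the objective does not promise. This stands in part. A table of counts that shows ongoing patients is a valid snapshot, but the plan does not commit to one, and a percentage pooled over unequal follow-up remains hard to interpret.
- **Detail is left to a later SAP.** Section 8.7 says so, and denominators are ordinary table-shell content. True, and nothing is foreclosed. But Section 8.7 sets the default, and its censoring-aware list omits even treatment duration.
- **The shift may be no larger than sampling error.** In the AE-early pattern at 12 to 66 months, the shifts are 2.3, 7.7 and 12.9 points. Taking 150 as one sample, about 135, 114 and 99 patients would have stopped, with 95% half-widths of about 7.3, 8.6 and 9.6 points. Only the last shift clearly exceeds its margin. This limits the urgency, although a larger sample would reduce the sampling error and not the shift.
- **The direction is unknown.** A reader might infer that AEs will be over-represented. That needs both a stopped-only denominator and AE stops that come earlier than other stops, and the documents state neither. The main sample also leaves out patients who stopped on 4/2 without switching, which may remove some early stops. This objection stands in full.

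**Conclusion.** The point holds as a conditional one. A primary-objective item is summarised by a method that takes no account of time, under follow-up that is unequal and possibly set site by site. The resulting percentages depend on follow-up and on a denominator the plan does not name. Under the assumptions above, about 13% to 47% would still be on sunitinib, and the AE share among stopped patients would be off by -8 to +13 points, or by nothing if the hazards are proportional.

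Three stronger readings are not supported. The documents do not show that AEs are over-represented. They do not say that patients will be on treatment at the cut; that is an inference from the dates, though a likely one. And they do not make the split between AE and progression the main tolerability result: primary objective 2 concerns treatment patterns, while AEs after the switch are a secondary objective. This is an inexpensive improvement to the analysis, not a defect that invalidates the study.

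**What to change.** In Section 8.7:

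- Add Aalen-Johansen cumulative incidence of stopping sunitinib by reason, from the start of the 2/1 schedule, separately for the switch sample and the Brazilian 2/1 starters, at fixed times such as 6, 12 and 24 months. Treat other reasons and death as competing events and censor patients still on sunitinib at last contact.
- Label the result as the probability of stopping for that reason by that time, not as the eventual share of stops.
- Keep the frequency table as counts over all patients, with rows for still on treatment and lost to follow-up.
- Reconcile Sections 3 and 8.7 on whether treatment duration is analysed by Kaplan-Meier.

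The cost is one standard SAS procedure and two table rows. Stop dates and reasons are already collected under Section 8.3.3, and death dates under Section 8.3.4. A date of last contact is not named in Section 8.3, but the planned Kaplan-Meier analysis of overall survival needs it in any case.

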1. Explore clinical outcomes after switching to the 2/1 schedule, including response to treatment, AEs, progression-free survival (PFS), and overall survival.
2. Describe demographic, clinical and treatment characteristics (eg, duration of treatment, reasons for stopping treatment), and clinical outcomes (eg, treatment response, AEs, PFS, and overall survival) among patients in Brazil who initiated first-line sunitinib treatment for metastatic RCC on the 2/1 schedule.

Study Design: Noninterventional, retrospective medical record review of patients with metastatic RCC who received first-line treatment with sunitinib and switched from the 4/2 to 2/1 administration schedule. A second sample of patients who initiated first-line treatment with sunitinib on the 2/1 schedule in Brazil will be collected and analyzed separately.

Population: Patients diagnosed with metastatic RCC with clear cell histology who switched from a 4/2 schedule to a 2/1 schedule of sunitinib in first-line metastatic treatment between January 1, 2014 and June 30, 2018. Patients must be aged 18 years or older at the time of the switch. The final dates defining this selection period will be dependent on country-specific ethics and reporting requirements. A second sample of adults who initiated first-line treatment with sunitinib on the 2/1 between January 1, 2014 and June 30, 2018 in Brazil will be collected and analyzed separately.

Variables: Patient characteristics, clinical characteristics, first-line treatment patterns, treatment-related outcomes, AEs, and survival.

Data Sources: Information will be abstracted from patients' medical records and compiled into an anonymized analytic database. All abstracted information will be retrospective.

Study Size: Data will be abstracted from a target of at least 150 medical records of patients treated at various sites across 7 Latin American countries.

[figure not shown]

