5. MILESTONES

Milestone	Planned date
Initiate feasibility assessment with sites after sites complete the confidentiality agreement with PPD	Q1 2019
Finalize study materials	Q2 2019
Initiate ethics review process after PPD contracts with a participating site	Q2 2019
Start of data collection	TBD (following completion of ethics review on a site-by-site basis)
Final interim analysis	Q3/Q4 2019
Final analytic results	TBD (based on site contracting timelines)
Final study report	TBD (based on site contracting timelines)

TBD = to be determined; Q = quarter; PPD

PFIZER CONFIDENTIAL

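### Section 8.7 leaves treatment duration, a primary-objective measure, off the Kaplan-Meier list on which the abstract places it

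*Combined protocol and SAP*

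**What the plan says.** Section 8.7 (Data Analysis) opens by summarising every Section 8.3 measure through "mean values, medians, ranges, and standard deviations of continuous variables of interest", with frequencies for categorical variables. It then states: "Time-to-event outcomes (ie, overall survival, PFS, time to second-line initiation) will be described using the Kaplan-Meier method". The Data Analysis paragraph of the abstract (Section 3) has a different list: "Time-to-event outcomes (ie, overall survival, treatment duration, PFS) will be described using the Kaplan-Meier method". Just before that, the abstract refers to "4/2, 4/1, and total treatment durations", although the study schedules everywhere else are 4/2 and 2/1.

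The second primary objective (Section 7) covers "total duration of sunitinib treatment, duration on the 4/2 schedule, duration on the 2/1 schedule". The secondary objective for the Brazil sample in the abstract reads in part "Describe demographic, clinical and treatment characteristics (eg, duration of treatment, reasons for stopping treatment". Section 8.3.3 derives durations from recorded start and stop dates. Section 8.7 also says that "Detailed methodology for summary and statistical analyses of data collected in this study will be documented in a statistical analysis plan".

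**The concern.** Each Kaplan-Meier list is introduced by *ie*, so each reads as complete, and they differ by one item in each direction. The abstract has treatment duration but not time to second-line initiation; 8.7 has the reverse. A programmer working from 8.7 would summarise duration like any other continuous variable.

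That is sound only if every patient's treatment has ended. If some are still on sunitinib when the record is read, their full duration is unknown. The simple mean is then too low, whether those patients are cut off at the last record or left out. The simple median of cut-off times is safe only if everyone is followed at least to the true median.

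Duration is one of the study's main products, and Section 6 offers the results as baseline measures against which later therapies could be compared. An understated duration would carry into those comparisons.

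**Working it through.** **Can treatment be ongoing at data cut-off?** Section 8.2.1 admits patients who start 2/1 from January 1, 2014 to June 30, 2018. Neither 8.2.1 nor 8.2.2 requires sunitinib to have stopped. The note to Figure 2 (Section 8.1) allows follow-up to end at a site's ethics approval, and Section 5 gives Q2 2019 for the step "Initiate ethics review process after PPD contracts with a participating site". With a mid-2019 cut-off, the last entrants have about 12 months of follow-up. Section 7 itself calls follow-up after the switch limited. So yes.

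**Which durations are affected?** Total duration and 2/1 duration. Initial 4/2 duration and time to switch are complete in the switch sample, because the switch is an entry criterion.

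**How large could the effect be?** The plan has no figure to reproduce, so this is an illustration. Assumed inputs:
- 2/1 duration is exponential with median 8, 11, 16 or 22 months. Eleven borrows the sunitinib median PFS cited in Section 6. The longer values are included because Section 6 cites a registry with treatment on 2/1 more than three times as long as on 4/2.
- Entry is spread over 54 months, either uniformly or with linearly rising density.
- Cut-off C is 66, 72 or 78 months after January 2014 (mid-2019, end 2019, mid-2020).

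Let m = median / ln 2 be the true mean and p the share ongoing at cut-off. For uniform entry:

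p = (m/54) × [exp(−(C−54)/m) − exp(−C/m)]

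The mean of times cut off at the last record is m(1 − p), so the simple mean is low by exactly the share ongoing.

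Median 11, C = 66: m = 15.87; p = 0.294 × (0.469 − 0.016) = 0.133. That is about 20 of 150 patients. The simple mean is 15.87 × 0.867 = 13.8 months against a true 15.9. With rising entry, p = 0.198 and the mean is 12.7.

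The simple median t solves exp(−t/m) × P(follow-up > t) = 0.5. The second factor is 1 up to C − 54 months, so the simple median is correct whenever the true median is at most 12, 18 or 24 months for the three cut-offs. Beyond that point the factor is (C − t)/54 for uniform entry, and its square for rising entry. Median 16, C = 66, uniform: t = 14.78, since 0.527 × 0.9485 = 0.500.

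Results for 2/1 duration (uniform / rising entry):

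| True median | Cut-off | Ongoing, and mean low by | Simple median low by |
|---|---|---|---|
| 8 | mid-2019 | 7% / 12% | 0 |
| 8 | mid-2020 | 3% / 4% | 0 |
| 11 | mid-2019 | 13% / 20% | 0 |
| 11 | end 2019 | 9% / 14% | 0 |
| 11 | mid-2020 | 6% / 9% | 0 |
| 16 | mid-2019 | 23% / 31% | 8% / 12% (14.8 / 14.1 months) |
| 16 | end 2019 | 18% / 24% | 0 |
| 16 | mid-2020 | 14% / 19% | 0 |
| 22 | mid-2019 | 33% / 42% | 18% / 25% |
| 22 | end 2019 | 27% / 35% | 7% / 10% |
| 22 | mid-2020 | 23% / 29% | 0 |

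**Total duration.** Add an independent, completed exponential 4/2 period to a 2/1 duration with median 11. At mid-2019, with a 3-month mean 4/2 period, the true mean is 18.9 months and the observed mean 16.8 / 15.7 (11% / 17% low). With a 6-month mean, it is 21.9 against 19.8 / 18.7 (10% / 14% low). The simple median is 1% to 4% low at mid-2019 and correct at the later cut-offs.

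**If patients without a stop date were dropped** (no section says so): at median 11 and mid-2019, the 2/1 mean is 25% / 35% low and the median 18% / 26% low.

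**Does Kaplan-Meier repair the median?** In 4,000 simulated samples of 150 at mid-2019, the Kaplan-Meier median averaged 11.1 for a true 11 (95% of samples about 8.8 to 13.7) and 16.1 for a true 16 (about 12.6 to 20.1). For a true 22 it averaged 22.1 / 22.3, where the simple median averaged 18.2 / 16.6.

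**The case against.** The abstract belongs to the same protocol and does assign Kaplan-Meier to duration. Section 8.7 never says that duration gets only the simple summary, and its opening sentence applies that summary to overall survival and PFS as well. The list of survival estimates in 8.3.4 is expressly open, and detailed methods are left to a later SAP that may modify the plan. On this view the two sentences need editorial alignment and no analysis is wrong.

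On size, the largest shortfalls concern the mean, which Kaplan-Meier does not recover in full. At 11 months, the only scale value taken from the documents, the 2/1 median is unaffected and the total-duration median moves by at most 4%. The 16- and 22-month values rest on a registry ratio with no baseline to multiply, and mid-2019 is the earliest plausible cut-off. The study is descriptive and tests nothing.

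Much of this stands. The figures are illustrative and shrink with later cut-offs, and the absence of event and censoring detail is not in itself an error at this stage. But 8.3.4 does not name duration, and 8.7, the section that governs the analysis, has a closed list without it. The SAP's author would inherit two conflicting lists for a primary-objective measure. In a descriptive study the estimate is the result, so its bias matters.

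**Conclusion.** The concern holds and should be fixed. The abstract and 8.7 contradict each other on the method for treatment duration, and 8.7 as written omits the method suited to patients still on treatment. The contradiction rests on the text alone.

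The numerical consequence depends on assumed durations, entry patterns and cut-offs. Over the assumed cases shown, with times kept and cut off at the last record, the mean of 2/1 duration is 3% to 42% low. The simple median is either correct or, when the true median exceeds the shortest follow-up, 7% to 25% low. If follow-up turns out long relative to treatment, the effect on the median vanishes and the effect on the mean becomes small. Initial 4/2 duration and time to switch are not affected.

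**What to change.** - In 8.7, add total first-line sunitinib duration and 2/1 duration to the Kaplan-Meier list, for both the switch sample and the Brazil sample.
- Make the abstract's list identical, including time to second-line initiation, and reconcile its reference to 4/1 with the schedules named elsewhere.
- Censor patients still on treatment at their last available record date. Report the Kaplan-Meier median with a 95% CI and the number still on treatment.
- Label any mean or SD of these two durations as observed time only, because Kaplan-Meier does not restore the full mean.
- Leave exact event definitions, such as the handling of death or a later schedule change, to the SAP.
- Confirm that the eCRF records the last-record date, which overall survival and PFS also need.

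The cost is one sentence each in 8.7 and the abstract, a few definitions in the SAP, and a routine Kaplan-Meier run on data already planned. The sample size does not change.
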